**Version 3.0**

**(Version date: 9/12/2024)**

**PI: [name]**

**Peking University People's Hospital**

## Historical versions

Version 3.0, September 12, 2024

• Add exploratory endpoints: the correlation between biomarkers with respond and outcomes) and revise the corresponding sections. Update sections: Study Synopsis , Section 2.1, Section 3.1, and Section 7.2.

Version 2.0, July 19, 2024

• Updated the time window for surgical treatment after neoadjuvant therapy and added method for ALK testing. Updated sections: Study Synopsis; Section 3.1.

• Updated the research schedule. Updated section: Section 3.1.

• Made additional minor changes and error corrections for clarity.

Version 1.0, April 10, 2024
Initial version.

## Study Synopsis

**Protocol Title:** *Phase II, Open-label, Single-arm, Prospective, Multi-center Study to evaluate the Efficacy and Safety of Lorlatinib as Neoadjuvant Treatment in Surgically Resectable Stage IB-IIIB ALK-rearranged Non-Small Cell Lung Cancer (NEOLORA)*

Study Sponsor(s):	Compound:
Peking University People's Hospital, [name]	Lorlatinib

### Background and Rationale

Lung cancer remains the foremost cause of cancer-related deaths worldwide, with non-small cell lung cancer (NSCLC) constituting approximately 80% of all lung cancer cases. Despite advancements, the prognosis for NSCLC patients, particularly those ineligible for surgical resection at diagnosis, is dismal, with median 5-year overall survival (OS) rates between 36% and 60%.

Currently, neoadjuvant (preoperative) platinum-based doublet chemotherapy regimens represent the standard care for resectable stage II or III NSCLC with oncogenic driver mutations. However, the marginal improvement in long-term survival underscores the critical need for more effective treatment strategies.

The discovery of driver mutations in NSCLC has revolutionized treatment approaches, with alterations in the anaplastic lymphoma kinase (ALK) gene being one of the significant breakthroughs. ALK rearrangements are identified in 3%-7% of NSCLC cases, guiding the development of targeted therapies. ALK inhibitors, including crizotinib, ceritinib, alectinib, brigatinib, and notably lorlatinib, have significantly impacted the treatment landscape of ALK-positive NSCLC by offering substantial improvements in survival and disease control.

Lorlatinib, a potent third-generation ALK inhibitor, is distinguished by its efficacy against a wide spectrum of ALK mutations, including those conferring resistance to earlier generations of ALK inhibitors. Its ability to cross the blood-brain barrier presents an added advantage for controlling central nervous system (CNS) metastases, a frequent challenge in NSCLC management. This profile, along with encouraging outcomes from phase I and II trials demonstrating lorlatinib's robust

antitumor activity in patients who have progressed on previous ALK TKI therapies, underscores its potential as a transformative neoadjuvant therapy option.

The advent of targeted therapies has markedly shifted the paradigm in the treatment of non-small cell lung cancer (NSCLC), particularly for patients with specific genetic alterations such as ALK rearrangements. A small retrospective study of the first-generation ALK-TKI crizotinib in the neoadjuvant setting included 11 ALK-positive, N2 NSCLC patients who received oral crizotinib (250mg twice daily) for a median duration of 30 days (range 28-120 days). This study demonstrated a 91.0% R0 resection rate with 18.2% (2 cases) achieving pathological complete response post-treatment. The SAKULA study, a phase II multicenter single-arm trial, assessed the efficacy and safety of the second-generation ALK-TKI ceritinib in resectable ALK-positive NSCLC. The study enrolled 7 cases all at stage IIIA (N2), and treated with oral ceritinib (750mg twice daily) as neoadjuvant therapy. The primary endpoint of major pathological response (MPR) was 57% (95% CI: 18-90), with 2 cases achieving complete remission (29%). NAUTIKA1, a phase II trial, investigated the efficacy of alectinib as neoadjuvant therapy for 8 weeks in patients with resectable stage II, IIIA, and IIIB NSCLC, followed by surgery, 4 cycles of adjuvant chemotherapy, and 2 years of alectinib adjuvant treatment. Among 9 patients, 6 achieved a major pathological response (MPR), resulting in an MPR rate of 66.7% (95%CI, 29.9%-92.5%), with a pathological complete response (pCR) rate of 33.3%. Eight patients underwent R0 resection. These results indicate the feasibility and potential efficacy of ALK-TKIs in improving surgical outcomes and reducing the tumor burden before surgery, making it a promising neoadjuvant treatment option for this patient population.

This study seeks to assess the feasibility of lorlatinib as neoadjuvant therapy for patients with resectable, stage IB-IIIB ALK+ lung adenocarcinoma. Given lorlatinib's advanced efficacy in targeting ALK-positive tumors, including its activity against resistant mutations and its proficiency in managing CNS metastases, this study aims to evaluate the efficacy and safety of lorlatinib as neoadjuvant therapy in patients, focusing on improvements in pathological response, surgical outcomes, prolonged survival, and safety/tolerability.

[figure not shown]
	Phase: Phase II
--	------------------------

## Study Design

Phase II, open-label, single-arm, prospective, multi-center Study

## Methods

Twenty-five patients with surgically resectable stage IB-IIIB ALK-rearranged NSCLC patients will be enrolled. These patients will receive lorlatinib neoadjuvant therapy for 6-8 weeks (determined by clinicians' decision based on clinical practice) and then underwent surgery. Eligible patients will be registered to receive oral lorlatinib 100mg qd for 6-8 weeks each during the neoadjuvant therapy phase. Neoadjuvant treatment response that will be assessed by the investigator using RECIST v1.1. If no progressive disease will be documented, candidates will undergo surgery with radical intent within 6 weeks after the completion of lorlatinib neoadjuvant therapy. Once patient complete surgery and pathological evaluation, she/he will remove from this study (within 1 month after surgery) and continue to receive treatment according to clinicians' decision based on clinical practice. All patients signed an informed consent prior to enrolment. Data will not be collected once patient withdrawal from this study.

## Primary Objectives

To explore the pathological complete response (pCR) of lorlatinib as neoadjuvant treatment

**Secondary Objectives**

To explore the major pathologic response (MPR) assessed by investigator ; objective response rate (ORR) per RECIST 1.1 , investigator-assessed ; surgical outcomes ; Safety and tolerability.

**Exploratory Objectives: Correlation between biomarkers with response and outcomes****Study Population**

Patients with ALK-rearranged, resectable stage IB-IIIB non-small cell lung cancer

Number of Subjects	Number of Sites:
25 patients	6 site in China
Dose Level(s):	Route of Administration:
Lorlatinib, 100mg, qd	Lorlatinib, oral
Duration of Treatment	Period of Evaluation
100mg, qd , 6-8 weeks	1 months
Main Criteria for Inclusion	

 
• Aged <math>\geq</math>18 years
 
• Imaging confirmed, resectable stage IB, II, IIIA or selected IIIB (including T4N2, per AJCC 8th edition)
 
• Histologically/cytologically confirmed lung adenocarcinoma
 
• Documented ALK-rearrangement mutation positive (assessed by a local laboratory)
 
• ECOG PS 0-1
 
• Patients must be treatment-naive for NSCLC and eligible to receive treatment with Lorlatinib.
 
• Measurable disease, as defined by RECIST v1.1
 
• Hematology, liver and kidney function are adequate for neoadjuvant therapy.
 
• Cardiopulmonary function suitable for surgical treatment (ECG, echocardiography, pulmonary function or blood gas analysis).
 
• Male participants must be willing to use acceptable methods of contraception.
 
• Female participants of childbearing potential must agree to use acceptable methods of contraception.
 
• Ability to provide written informed consent.
 
	

### **Main Criteria for Exclusion**

- Mixed squamous cell carcinoma, large cell carcinoma, small cell lung cancer.
- Prior treatment with any systemic anti-cancer therapy for locally advanced NSCLC
- Non-resectable stage IB, II, IIIA or selected IIIB NSCLC evaluated by thoracic surgeons.
- Unable to tolerate curative surgery per anaesthesiologist evaluation. History of organ transplant.
- Pregnant or lactating, or intending to become pregnant during the study
- Evidence of any severe or uncontrolled systemic disease, including uncontrolled hypertension and active bleeding, that the investigator considers to be detrimental to patient participation in the study or to adherence to the protocol.
- Past medical history of Interstitial lung disease (ILD), drug-induced ILD, radiation pneumonitis which required steroid treatment, or any evidence of clinically active ILD.
- A clear past history of neurological or psychiatric disorders, including epilepsy or dementia;
- Judgement by investigator that the subject should not participate in the study if the subject is unlikely to comply with the study procedures, restrictions and requirements.

## **Main Criteria for Evaluation and Analyses**

**Primary endpoint:** Pathologic complete response (pCR) assessed by investigator.

**Secondary endpoints:**

- Major pathologic response (MPR) assessed by investigator (defined as no more than 10% residual viable tumor cells in the surgical specimen).
- Objective response rate (ORR) per RECIST 1.1, investigator-assessed;
- Surgical outcomes and intraoperative events
- Rate of lymph node downstaging;
- Unanticipated delays to surgery;
- Surgical complication rate;
- Safety and tolerability per NCI-CTCAE v5.0.

**Exploratory endpoints:** Correlation between biomarkers with response and outcomes

Efficacy analysis set include all patients who received at least one dose of lorlatinib.

Safety analysis set include all patients who received at least one dose of lorlatinib and had the post-treatment safety assessment.

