##### *Full-Analysis-Set (FAS) Population*

The FAS will include all participants who are enrolled. The FAS will be the primary population for evaluating all efficacy endpoints and participant characteristics.

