##### *Safety-Analysis-Set (SAT) Population*

The SAT Population will include all subjects who receive at least 1 dose of study medication. The SAT Population will be the primary population for evaluating

treatment administration/compliance and safety. Efficacy endpoints may be assessed in this population as well.

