#### **9.2.5 Analysis of Secondary Endpoints**

All analyses will be performed using the FAS.

Objective Response on each treatment arm will be summarized based on the investigator's assessment. The number and percent of subjects achieving objective response (CR or PR) will be summarized along with corresponding 2-sided 95% CI using the binomial distribution.

MPR rate refers to the proportion of patients  $\leq 10\%$  residual viable tumor cells histologically detected in the resected primary tumor and all resected lymph nodes after surgery assessed by the investigator.

Descriptive data analyses will be conducted for both primary and secondary objectives. Categorical variables will be summarized including the number of non-missing observations, the frequency of the observed endpoint as well as the observed proportion. Continuous variables will be summarized including the number of non-missing observations, mean (Standard Deviation [SD]), median, Q1, Q3, and the minimum/maximum.

- MPR, and ORR will be summarized using frequency counts and percentages with 95% CIs.
- Continuous variables in surgical outcomes will be summarized using median and range.

Categorical variables in surgical outcomes, safety and tolerability will be summarized using frequency counts and percentages.

Descriptive statistics will be used to summarize subject characteristics, study conduct, subject disposition, treatment administration/compliance, and safety parameters.

Data will also be displayed graphically, where appropriate.

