### **9.3 Safety Analysis**

The SAT Population will be the primary population for evaluating safety.

All subjects who receive at least one dose of study medication will be included in the summaries and listings of safety data. The overall safety profile and toleration of lorlatinib will be characterized by type, frequency, severity (as graded by CTCAE v5.0), timing and relationship of study treatment of AEs and laboratory abnormalities, by

treatment arm, as appropriate.

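### The synopsis and section 9 define both the efficacy set (dosed versus enrolled) and the safety set (dosed and assessed versus dosed only) differently

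*Protocol*

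**What the plan says.** **Efficacy set.** The Study Synopsis, after its list of secondary endpoints, states: "Efficacy analysis set include all patients who received at least one dose of lorlatinib". Section 9.2.1 states: "The FAS will include all participants who are enrolled", and continues: "The FAS will be the primary population for evaluating all efficacy endpoints and participant characteristics". Section 9.2.5 says of the secondary endpoints: "All analyses will be performed using the FAS".

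**Safety set.** The synopsis limits the set to patients who "received at least one dose of lorlatinib and had the post-treatment safety assessment". Section 9.2.1 states: "The SAT Population will include all subjects who receive at least 1 dose of study medication". Section 9.3 agrees with 9.2.1: "All subjects who receive at least one dose of study medication will be included in the summaries and listings of safety data". For this dosed population, 9.2.1 adds: "Efficacy endpoints may be assessed in this population as well".

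All of this is current text. No section says whether the synopsis or the body prevails, and none defines enrolment as receipt of a first dose.

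**The concern.** The protocol fixes two different populations for the primary endpoint. The synopsis efficacy set is the same group as the section 9.2.1 safety population, where efficacy analysis is only an optional addition. The one efficacy set that the synopsis names is therefore supplementary in the body. A patient enrolled but never dosed is in the denominator of pCR, MPR and ORR under section 9 and out of it under the synopsis.

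The extra safety condition is the more awkward one. The synopsis does not say what the post-treatment safety assessment is. It could be any safety check after the first dose. It could also be the Post-Treatment Follow-up Visit, which Table 1 footnote 13 and section 6.4.6 place 28 to 35 days after treatment ends. Either way the condition can remove dosed patients who die or leave before being assessed, and these may be the patients who tolerated the drug worst. The second reading would remove more of them.

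This is not a detail left to the SAP. The protocol states incompatible definitions, and if they stand, the choice could be made after the data are known.

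**Working it through.** **1. Definitions side by side**

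| Set | Synopsis | Section 9 |
|---|---|---|
| Efficacy | at least one dose | all enrolled (9.2.1, 9.2.5) |
| Safety | at least one dose and the post-treatment safety assessment | at least one dose (9.2.1, 9.3) |

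The efficacy sets differ by patients enrolled but never dosed. Section 6.3 assigns lorlatinib after screening and baseline, with treatment to start within 3 days, so such a patient is possible but should be rare. The safety sets differ by patients dosed but not assessed.

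**2. The plan's own design figure (section 9.1)**

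Inputs: 15 patients in stage 1, stop at 1 or fewer pCRs; 25 in total, reject at 6 or more; null rate 10%, alternative 30%.

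P(reject | p) = Σ (x = 2 to 15) C(15, x) pˣ (1 − p)¹⁵⁻ˣ × P[Bin(10, p) ≥ 6 − x]

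- p = 0.10: 0.033, within the stated 0.05 limit.
- p = 0.30: 0.802, against the stated 0.80.

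A search over designs with these limits returns this one as minimax, so the stated design reproduces.

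**3. Efficacy denominator**

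The protocol gives no number of undosed patients. I assume 0, 1 or 2 of 25, and I assume Clopper-Pearson intervals: lower limit = Beta⁻¹(0.025; x, n − x + 1), upper limit = Beta⁻¹(0.975; x + 1, n − x).

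| Never dosed | pCR / n | Rate | 95% CI |
|---|---|---|---|
| 0 (also section 9 in every case) | 6/25 | 24.0% | 9.4 to 45.1 |
| 1 (synopsis) | 6/24 | 25.0% | 9.8 to 46.7 |
| 2 (synopsis) | 6/23 | 26.1% | 10.2 to 48.4 |

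Near one half, 12/25 = 48.0% (27.8 to 68.7) becomes 12/24 = 50.0% (29.1 to 70.9).

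**4. Safety denominator**

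Assume 25 dosed patients, one of whom lacks the assessment.

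| Assumed event | Section 9 | Synopsis |
|---|---|---|
| That patient is the only death | 1/25 = 4.0% (0.1 to 20.4) | 0/24 = 0% (0 to 14.2) |
| That patient is one of 5 with a severe event | 5/25 = 20.0% (6.8 to 40.7) | 4/24 = 16.7% (4.7 to 37.4) |

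**5. The decision rule**

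With accrual fixed at 25 enrolled, the rule counts pCRs and an undosed patient cannot add one, so the choice of set does not change the decision. However, 9.1 does not say whether its 15 and 25 patients are enrolled or dosed. If 25 are enrolled, the cut-off of 6 is kept and the undosed patients all fall in stage 2, the same formula with a smaller second stage gives power at 30% of 0.768 with 24 dosed and 0.729 with 23. If 25 dosed patients are accrued, power stays at 0.802.

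**The case against.** The best counter-argument is that the difference will hardly ever bite. In a single-arm, open-label trial with treatment due within 3 days of completed baseline, enrolled and dosed should nearly coincide, and one undosed patient moves the pCR rate by one percentage point inside an interval more than 35 points wide. That is right, and the efficacy part should be read as small.

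On safety, the ordinary reading of the synopsis phrase is any check after dosing starts. Adverse events are collected at Day 15, at later cycle visits, at end of treatment and at follow-up, so only a patient with no post-dose safety data would drop out. This also has force: the severe-event example fits the visit-specific reading better. A death before the first post-dose check would still be lost from the rate on the ordinary reading. The death would not go unreported, because section 8.1 requires SAE reporting to 28 days after the last dose, but it could leave the rate table.

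It can also be said that a synopsis is only a summary. The protocol does not say that the body prevails, and this synopsis is not a shortened form of section 9: it uses another efficacy criterion and adds a safety condition that section 9 does not contain. The permission in 9.2.1 to look at efficacy in the dosed population does not remove the conflict, since the full analysis set stays primary there.

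**Conclusion.** The concern holds. Both sets are defined in two ways that cannot both be followed. The efficacy conflict reaches the primary endpoint, but its expected effect is small: about one percentage point on the pCR rate per undosed patient at 6 pCRs. The safety conflict can change a result in kind, from one death to none, if a dosed patient dies before the assessment. All these sizes rest on assumed counts, and they are zero if every enrolled patient is dosed and assessed. The pass or fail decision is unchanged if the 25 are counted as enrolled patients. This should be fixed; it does not undermine the design.

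**What to change.** Align the synopsis with section 9.2.1 and use one definition per set throughout.

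- **Efficacy:** the full analysis set, all enrolled participants. The dosed population serves only as the supplementary analysis that 9.2.1 already allows.
- **Safety:** all patients with at least one dose. Delete the post-treatment assessment condition from the synopsis.

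Section 9.2.3 may also name the full analysis set for pCR. How to count patients without a resection specimen is a separate question that this correction does not depend on.

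The cost is synopsis wording and, if wanted, one sentence in 9.2.3. No new data are needed and the Simon boundaries do not change. Reported efficacy rates may be slightly lower than on the dosed set.

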## **Statistical Considerations**

Detailed methodology for summary and statistical analyses of data collected in this study will be documented in a Statistical Analysis Plan (SAP).

## **Sample Size Determination**

According to the Simon's 2-stage mini-max design, the null hypothesis that the PCR rate is  $\leq 10\%$  will be tested against a 1-sided alternative. In the first stage, 15 patients will be accrued. If there are 1 or fewer PCR in these 15 patients, the study will be stopped early for futility. Otherwise, 10 additional patients will be accrued for a total of 25. The null hypothesis will be rejected if 6 or more PCR are observed in 25 patients. This design yields a type I error rate of 0.05 and power of 0.80 when the true PCR rate is 30%.

## **Statistical Analyses-Preliminary Descriptive Analysis**

Descriptive data analyses will be conducted for both primary and secondary objectives. Categorical variables will be summarized including the number of non-missing observations, the frequency of the observed endpoint as well as the observed proportion. Continuous variables will be summarized including the number of non-missing observations, mean (Standard Deviation [SD]), median, Q1, Q3, and the minimum/maximum.

- PCR, MPR, and ORR will be summarized using frequency counts and percentages with 95% CIs.
- Continuous variables in surgical outcomes will be summarized using median and range.
- Categorical variables in surgical outcomes, safety and tolerability will be summarized using frequency counts and percentages.

## **Collection of Biological Specimens**

Collection of tissue samples in this study:

For patients meeting the inclusion criteria, tissue samples will be collected at baseline and post-operation. This includes tissue specimens in paraffin blocks or formalin-fixed samples, or fresh tissue.

Collection of blood samples in this study:

For patients meeting the inclusion criteria, blood samples will be collected at baseline, 2 weeks, 4 weeks, and end of neoadjuvant therapy, pre-operation, 3 days and 1-month post-operation, with each collection involving 20 mL of blood.

### **Sample Size Justification**

Twenty-five patients will be involved in this study.

Detailed methodology for summary and statistical analyses of data collected in this study will be documented in a Statistical Analysis Plan (SAP).

## 1. INTRODUCTION

Lung cancer is the most fatal malignancy in China, as estimated by National Cancer Center of China, accounting for 1,060,600 new cases, and 733,300 deaths in 2022. Non-small cell lung cancer (NSCLC), constituting 80%-85% of lung cancer, is most often diagnosed in advanced stages, where surgery and local radiotherapy are no longer curative or indicated. A critical molecular subset characterized by rearrangements in the anaplastic lymphoma kinase (ALK) gene represents a distinct clinical and pathological entity. These ALK rearrangements are identified in 3-7% of NSCLC patients, often manifesting in younger individuals, non-smokers or light smokers, and predominantly in those with adenocarcinoma histology. The management of early-stage NSCLC, particularly stages I to IIIA, primarily involves surgical resection with curative intent, frequently complemented by adjuvant therapy to diminish the risk of disease recurrence.

Despite the availability of surgery and perioperative therapy, the recurrence rates in early-stage NSCLC remain significant, underscoring a considerable unmet clinical need for more effective and targeted therapeutic strategies. The five-year survival rates for patients with resected NSCLC are approximately 36%-60%, highlighting the imperative for innovative treatment approaches that can improve these outcomes. Currently, platinum-based doublet chemotherapy regimens represent the standard care for driver gene positivity resectable stage II or IIIA NSCLC, however, the marginal improvement in long-term survival underscores the critical need for more effective treatment strategies.

The discovery of ALK rearrangements in NSCLC has ushered in an era of targeted therapy, with ALK tyrosine kinase inhibitors (TKIs) significantly altering the

treatment landscape. ALK TKIs, including crizotinib, ceritinib, alectinib, brigatinib, and notably lorlatinib, have significantly impacted the treatment landscape of ALK-positive NSCLC by offering substantial improvements in survival and disease control. These agents have demonstrated remarkable efficacy in the advanced disease setting, leading to interest in their potential application earlier in the disease course, including the neoadjuvant setting. Neoadjuvant therapy with ALK-TKIs presents an opportunity to reduce tumor size and possibly improve surgical outcomes, while simultaneously addressing micrometastatic disease.

A small retrospective study of the first-generation ALK-TKI crizotinib in the neoadjuvant setting included 11 ALK-positive, N2 NSCLC patients who received oral crizotinib (250mg twice daily) for a median duration of 30 days (range 28-120 days). This study demonstrated a 91.0% R0 resection rate with 18.2% (2 cases) achieving pathological complete response post-treatment. The SAKULA study, a phase II multicenter single-arm trial, assessed the efficacy and safety of the second-generation ALK-TKI ceritinib in resectable ALK-positive NSCLC. The study enrolled 7 cases all at stage IIIA (N2), and treated with oral ceritinib (750mg twice daily) as neoadjuvant therapy. The primary endpoint of major pathological response (MPR) was 57% (95% CI: 18-90), with 2 cases achieving complete remission (29%). NAUTIKA1, a phase II trial, investigated the efficacy of alectinib as neoadjuvant therapy for 8 weeks in patients with resectable stage II, IIIA, and IIIB NSCLC, followed by surgery, 4 cycles of adjuvant chemotherapy, and 2 years of alectinib adjuvant treatment. Among 9 patients, 6 achieved a major pathological response (MPR), resulting in an MPR rate of 66.7% (95%CI, 29.9%-92.5%), with a pathological complete response (pCR) rate of 33.3%. Eight patients underwent R0 resection. These results indicate the feasibility and potential efficacy of ALK-TKIs in improving surgical outcomes and reducing the tumor burden before surgery, making it a promising neoadjuvant treatment option for this patient population.

Lorlatinib, a potent third-generation ALK inhibitor, is distinguished by its efficacy against a wide spectrum of ALK mutations, including those conferring resistance to

earlier generations of ALK inhibitors. Clinical trials evaluating lorlatinib in ALK-positive advanced NSCLC patients, including first-line patients, those with CNS metastases and who have developed resistance to earlier-generation ALK-TKIs, have showcased its considerable efficacy and manageable safety profile. Lorlatinib's broad activity spectrum and CNS penetration capabilities uniquely position it as a promising candidate for exploration in the neoadjuvant setting.

Building upon the therapeutic successes of ALK-TKIs in the metastatic and adjuvant settings, the potential application of lorlatinib as a neoadjuvant therapy warrants thorough investigation. The neoadjuvant approach with lorlatinib aims to exploit its potent antitumor activity against ALK-driven NSCLC to achieve significant tumor shrinkage, potentially facilitating more effective surgical resections and improving postoperative outcomes. Moreover, this strategy offers the opportunity to address micrometastatic disease early in the treatment continuum, which could translate into prolonged disease-free and overall survival rates for patients. Drawing parallels from the clinical outcomes associated with these agents, lorlatinib's superior pharmacological profile suggests that it could offer enhanced efficacy in reducing primary tumor size, achieving higher rates of complete pathological response, and potentially extending survival in patients with early-stage, resectable NSCLC harboring ALK rearrangements.

